Potential participants are identified using medical chart and case review. The study eligibility requirements will be reviewed by the PI and study staff. The potential participant is pre-selected as tentatively meeting the eligibility requirements for the study. Research study staff will reach out to eligible patients through a phone call explaining the study. Randomization to the treatment (KRONOS postoperative brace) or control group (Hinged knee brace) will occur at the time of informed consent

Informed Consent Discussion

Investigator and/or PI and research study staff will contact the patient in clinic or via telephone to discuss the research study with them. Ideally, the informed consent discussion should be conducted when the study staff and potential participant has time to ask and answer questions. Information provided to the patient includes the rationale for the study procedure or treatment, the number of study visits and the study activities they will need to complete, risks involved, expected benefits, and alternatives to treatment.

The process may occur over a period of several discussions, culminating in the signing of a consent form in the office (Ipad or paper) or sent to their verified email address. The informed consent discussion will be documented in the patient profile or chart.

If the patient agrees to participate, their email addressed will be verified. The consent will be obtained electronically sent through the secured platform called Patient IQ to their email. The potential subject will then be prompted to reply with the appropriate passcode in order to access the consent form, and then provide the passcode again with their

Version 2.0: 4/25/2025 Page 4 of 11

signature (secured). No research activities will be performed prior to execution of the consent. A copy of the time stamped document will be sent to the study team through the electronic platform and a copy will be sent to the participant.

Study Design & Procedures-

This is a randomized controlled trial.

We estimate 40 participants (20 Kronos: 20 T-Scope) will be enrolled in the study.

Primary outcome variable

• Rates of extension deficit (as measured by the fraction of patients with reduced extension compared to the contralateral knee, determined by heel height and goniometric measurements of knee extension)

Bracing Protocol

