Both treatment groups will progress according to a standard of care postoperative rehabilitation program regardless of the group to which the patient is randomized.

KRONOS Bracing Group

Subjects randomized to the treatment group will be measured and fitted with the KRONOS knee brace at their initial clinic visit after study enrollment. The patient will be instructed to use the brace preoperatively and bring it to their surgery, after which the brace will be placed again on the patient postoperatively at the conclusion of their procedure. Subjects will be instructed to wear the brace until symmetric terminal extension is achieved as indicated by side-to-side comparison with the non-surgical limb. This will be under the supervision and approval of the providing physician. Subjects will be instructed to use the brace (locked in extension and under high tension) at night during sleep and ambulation, though removal for therapy and rehabilitation exercises will be permitted.

Control Group – Standard Breg T-Scope Postoperative Bracing

Subjects will be placed in a standard postoperative hinged knee brace in the operating room that will be locked in full extension. Subjects will be instructed to use the brace locked in extension while sleeping for 6 weeks and when ambulating until the patient is able to perform a straight leg raise with no extension lag outside of the brace, at which point the brace may be worn unlocked during ambulation.

Table 1. Study timeline.

Preop Surgery 2 6 weeks 12 6 months 12

Version 2.0: 4/25/2025 Page 5 of 11

			weeks		weeks		months
Patient Recruitment	•						
Informed Consent and Randomization Physical Exam (i.e. Heel height and	•						
goniometer measurement of active	•	•*	•	•	•	•	
extension, passive flexion, passive extension)							
Circumferential thigh							
measurement (including healthy	•		•	•	•	•	
knee at pre-op)							
Brace Placement	•**	•					
PROMs	•				•	•	•
Brace compliance survey	1 .	•**	•	•	.1	. 1	

^{*}Passive flexion and extension ROM only under anesthesia prior to beginning surgery

PROMs will include: IKDC, KOOS, VR-12, PROMIS Depression, PROMIS Physical Function, PROMIS Pain Interference, Return to Sport (RTS) and Return to Work (RTW), Resilience scale and brace compliance survey.

Study Interventions –

Prospective Data Collection

Timeline of Events

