- 1. Once subjects are indicated for ACL surgery, a review of inclusion criteria will be undertaken, and subjects will be offered the opportunity to participate in the study.
- 2. Pre-operative physical exam findings including Pivot-shift, Lachman, and range of motion data will be recorded.
- 3. Range of motion measurements (ROM), including heel height^{7,8} and goniometric measurements of 3 types of ROM (active extension, passive flexion, and passive extension) will be done at the initial visit, preoperatively on the day of surgery, *intraoperatively under anesthesia before the initiation of the surgery* (passive flexion and passive extension only), and at the designated postoperative timepoints indicated in Table 1 (1 week, 2 week, 6 week, 12 weeks, 6 months, and 12 months).
- 4. Thigh circumference will also be measured with tape measure at the mid-thigh and

Version 2.0: 4/25/2025 Page 6 of 11

^{**} Only for patients randomized to the KRONOS brace treatment group

suprapatellar levels on the operative knee as a surrogate for quadriceps atrophy, as previously done^{10–12}, pre-operatively and at the designated postoperative visits in Table 1 (1 week, 2 week, 6 week, 12 weeks, 6 months, and 12 months). Thigh circumference of the nonoperative healthy knee will also be measured pre-operatively for baseline comparison

- 5. Informed consent will be obtained. Prior to surgery (preoperative) subjects will be asked to complete standard of care patient reported outcomes questionnaires including IKDC, KOOS, PROMIS (Depression, Pain Interference, Physical function), VAS pain, VR/SF 12, RTS, RTW and brief resilience scale.
- 6. Brace compliance survey A survey assessing patient compliance with bracing instructions will be administered at the designated postoperative timepoints indicated in Table 1.
- 7. Subjects will proceed with operative management of their ACL tear, including appropriate treatment and documentation of concomitant injuries.
- 8. Subjects will be appropriately fitted for the brace corresponding to randomization on the day of surgery. All braces will be placed on the subject in the operating room at the conclusion of the procedure. All subjects will begin a standard of care physical therapy protocol on postoperative day 1-14.

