- 9. Subjects will undergo standard of care follow up at 1-week, 2-week, 6-weeks, 12-weeks, 6-months, and 12 months. At these standard of care visits, range of motion, including goniometric angle and heel-height measurements, will be made at all postoperative time points.

 Time-to-achievement of full symmetric extension relative to the non-surgical knee will be monitor and recorded. Additional physical exam of the knee will be performed at all follow-up time points.
- 10. At 12 weeks, 6 months, and 12 months, subjects will also be asked to complete standard of care patient reported outcomes questionnaires including IKDC, KOOS, PROMIS, VAS pain, VR/SF 12, and brief resilience scale. Subjects will also be asked to answer standard of care questions regarding return to work and return to sport throughout the 1-year postoperative period.

Retrospective Data Collection

The following data will be abstracted from secured electronic medical record databases (Epic, Athena, Opal, Patient IQ) and electronically recorded on coded data collection tool for this study:

- Demographic information (age, sex, body mass indes (BMI), laterality)
- Chief Complaint
- History of present illness

Version 2.0: 4/25/2025 Page 7 of 11

Physical Exam

Opal and Joints will be used to capture the following:

Surgical approach

Arthroscopic diagnoses

Techniques used

Fixation device / technique

Preoperative imaging including but not limited to MRI

The following outcome variables will be taken from Athena and Patient IQ:

- Postoperative complications
- Failure of primary reconstruction
- Need for a revision or subsequent procedure
- Preoperative / postoperative patient reported outcomes (PRO) including:

IKDC, KOOS, VR-12, PROMIS Depression, PROMIS Physical Function, PROMIS

Pain Interference, Return to Sport (RTS) and Return to Work (RTW), Resilience scale

Other outcomes variables of interest:

- Time-to-achievement of full extension
- Degree of extension loss
- Time to walking without a limp
- Quad circumference difference
- Frequency of brace use
- Number of postoperative physical therapy visits up to one year post-op
- Standard of care Breg T-scope group: time to unlocking the brace
- Kronos group: time to no quad assist (no dial engaged)

Rehabilitation Protocol

The rehabilitation program will be started on the day after surgery according to the providing physician's standard protocol.

Risk/benefit assessment –

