There is no direct benefit to the patient for his/her participation in this study.

The results will contribute to the optimization postoperative bracing and rehabilitation protocols following ACL surgery. This study will help determine if the KRONOS postoperative knee brace is an efficacious and safe methodology to improve range of motion and reduce extension deficits following ACL reconstruction.

Version 2.0: 4/25/2025 Page 8 of 11

Potential risk may include having the participant's privacy or confidentiality compromised. The participant's identities will not be identifiable in publications resulting from this investigation. Every reasonable effort will be made to protect the participant's information while their data is used as part of this study.

The alternative to participation in this study is not to participate.

Costs to the subject—

A brace will be provided to each study participant free of cost regardless of what group they are in—a standard of care Breg T-Scope brace or a Kronos brace.

No insurance coverage will be offered for regularly scheduled standard of care postoperative visits. However, any additional visits scheduled solely for the purpose of this study will be covered at no cost to the patient.

Compensation of subjects-

No compensation will be offered to study participants.

Data Analysis and Statistical Considerations -

Power analysis was based on data published by Mikkelsen et al.⁶ as part of an ACLR randomized controlled trial of a hyperextension brace. A priori power analysis was conducted to determine the sample size required to detect a significant difference in the proportion of patients experiencing a loss of full knee extension of $\geq 2^{\circ}$ between the straight brace and hyperextension brace groups. Using the observed proportions from the study (p1=0.545 for the extension group and p2=0.091 for the hyperextension group), the following parameters were used in G*Power for the calculation: **Statistical test**: Fisher's exact test (two independent groups); **Effect size**: w=0.57; **Significance level** (α): 0.05; **Power** ($1-\beta$): 0.8. The analysis indicated that a total sample size of 32 **participants** (16 per group) would be required to achieve 80% power to detect a statistically significant difference in the proportions of patients experiencing knee extension loss at $\alpha=0.05$. To account for potential loss of subjects to follow-up, a total of 40 subjects will be eligible to be enrolled.

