The statistical software *R* will be used for analyses and calculation of relevant p-values, standard deviation, correlation coefficients, and confidence intervals. Categorical variables will be analyzed via Chi-squared test, while quantitative variables will be analyzed via students' t-test for parametric data and Wilcoxon Mann-Whitney test for nonparametric data.

Data & Safety monitoring

Version 2.0: 4/25/2025

There is minimal risk to the subjects except the potential for loss of privacy and confidentiality, but every reasonable effort will be made to protect the patient's information while their data is used as part of this study.

Data storage & confidentiality –

Participant information will be collected and maintained in a excel data sheet housed on the Midwest Orthopedics at Rush (MOR) server, which is dual-factor authentication protected and accessible only to research staff. Subjects identity will be coded via the use of a separate document key (electronic excel spreadsheet) correlating subjects' Rush medical record numbers with a study ID assigned for the sole purpose of this study. This key electronic document will be maintained as a separate electronic file (excel spreadsheet) from data collection tool and will be housed in the Midwest Orthopaedics at Rush server, which is dual-factor authentication protected and accessible only to research staff.

Files will not be shared with non-study personnel.

According to (Rush policy OP-0432 and CC-G04) and study data must be maintained for 10 years in accordance with Illinois State Law. After this time the data will be destroyed by permanently and securely deleting electronic files on the Master key document (PHI) and the coded data collection tool.

References:

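### The healthy thigh is taped only before surgery, so later girth loss in the operated thigh cannot be told apart from general girth change

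*Protocol*

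**What the plan says.** Protocol, Timeline of Events, item 4, has thigh girth taped at mid-thigh and at "suprapatellar levels on the operative knee as a surrogate for quadriceps atrophy". The operated thigh is measured "pre-operatively and at the designated postoperative visits in Table 1 (1 week, 2 week, 6 week, 12 weeks, 6 months, and 12 months". For the other leg the same item says: "Thigh circumference of the nonoperative healthy knee will also be measured pre-operatively for baseline comparison". The thigh row of Table 1 carries the same restriction: it reads "measurement (including healthy" and goes on to name the pre-op visit only.

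The outcome these data feed is listed under Other outcomes variables of interest as "Quad circumference difference". The protocol does not say whether this means operated minus healthy, or change in the operated thigh from its own preoperative value. Under Data Analysis and Statistical Considerations, "quantitative variables will be analyzed via students' t-test for parametric data", with a Mann-Whitney test otherwise.

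**The concern.** Girth is offered as a stand-in for quadriceps atrophy, and the protocol lists no other atrophy measure. Girth also moves with body weight, activity and general deconditioning, which affect both thighs. Taping the other thigh at the same visit is the direct way to see how much of a change is common to both legs. The planned schedule has no such measurement after surgery.

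What is at stake is interpretation first and precision second. A fall in operated-thigh girth could be local muscle loss, general change or both. The Background section expects the KRONOS brace to speed the return to activity, so general change could plausibly differ between arms and be read as a local quadriceps effect. With about 20 patients per arm, avoidable noise is also unwelcome. Because this is a data-collection choice, a later analysis plan cannot repair it.

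**Working it through.** **Which quantities can be formed.** Let O be the operated and H the healthy thigh, with 0 for pre-op and t for a postoperative visit. Let g be girth change common to both thighs and a the change specific to the operated thigh:

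- O_t = O_0 + g + a
- H_t = H_0 + g

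The plan collects O_0, H_0 and O_t, but not H_t. The candidate outcomes are:

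- Change from own baseline: O_t − O_0 = g + a (available).
- Side difference, preoperative reference: O_t − H_0 = (O_0 − H_0) + g + a (available).
- Side difference, same visit: O_t − H_t = (O_0 − H_0) + a (not available).

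Both available quantities contain g + a, and nothing collected separates the two. At the last visit in item 4 the healthy-leg reference is about 12 months old.

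**Precision.** The protocol gives no SD, correlation, effect size or power for thigh girth, so there is no stated figure to reproduce. Inputs:

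- 20 per arm, from Study Design & Procedures: "We estimate 40 participants (20 Kronos: 20 T-Scope) will be enrolled in the study".
- Two-sided alpha 0.05 and 80% power, used for illustration. The protocol states these values for the primary outcome and does not give the sidedness.
- Assumed: equal SD s for both thighs, with s = 5 cm for scale.
- Assumed: rt, the correlation of O_t with H_t, is 0.95.
- Assumed: r0, the correlation of O_t with H_0, is between 0.90 and 0.95.

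Formulas:

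- Var(O_t − H_0) = 2s²(1 − r0)
- Var(O_t − H_t) = 2s²(1 − rt)
- Penalty = 2s²(rt − r0); ratio = (1 − r0)/(1 − rt)
- Detectable difference = (1.960 + 0.842) × √(2/20) × SD of the difference = 0.886 × SD

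| r0 (rt = 0.95) | SD of difference, s = 5 cm | Variance ratio | Detectable difference |
|---|---|---|---|
| 0.95 | 5√0.10 = 1.58 cm | 0.05/0.05 = 1.0 | 1.40 cm |
| 0.93 | 5√0.14 = 1.87 cm | 0.07/0.05 = 1.4 | 1.66 cm |
| 0.90 | 5√0.20 = 2.24 cm | 0.10/0.05 = 2.0 | 1.98 cm |

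The first row is also the same-visit case, so it shows no loss. The ratios do not depend on s.

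**What the ratios imply.** In general, Var(O_t − H_0) = Var(O_t − H_t) + Var(g) + 2Cov(O_t − H_t, g). If common change is unrelated to the side difference, the covariance is zero and the old reference can only add variance. The same-visit variance is 1.58² = 2.5 cm². A ratio of 1.4 then needs Var(g) = 0.4 × 2.5 = 1.0 cm², an SD of 1.0 cm. A ratio of 2.0 needs Var(g) = 2.5 cm², an SD of 1.58 cm. An SD of 0.5 cm gives (2.5 + 0.25)/2.5 = 1.1.

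**The case against.** The strongest case for the plan is that a fixed preoperative reference is defensible. The healthy thigh can itself change after surgery. If it has its own change b, the same-visit difference becomes (O_0 − H_0) + a − b, which hides atrophy when both legs lose girth and could cancel part of a real brace effect. A preoperative value cannot be altered in this way. This stands, and it is why the same-visit difference should be added and not substituted.

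The outcome is also one of several secondary variables. The sample size, stated as "required to achieve 80% power to detect a statistically significant difference", concerns extension loss only. Item 4 and Table 1 agree on the healthy-leg timing, so there is no contradiction. Leaving the definition of a derived variable to the analysis plan is common and is not the fault here.

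A reader might infer more than the documents support:

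- **That the outcome uses an outdated reference.** It is undefined. If it is change from the operated leg's own baseline, the healthy thigh does not enter and that variance penalty does not arise, although g remains.
- **That precision equal to 29–50% of the patients is lost.** That is 1 − 1/1.4 and 1 − 1/2.0, and it follows only from choosing r0 below rt. At equal correlations the loss is zero.
- **That the arms are compared with bias.** Both follow the same schedule, so general change unrelated to the brace adds at most noise to the randomized comparison.
- **That this departs from a same-visit standard set for the primary outcome.** The primary outcome refers to the contralateral knee, but item 3 does not say when that knee is measured.

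**Conclusion.** The point holds as a limit of the measurement schedule. After surgery no same-visit side-to-side thigh difference can be formed, and neither quantity that can be formed separates operated-leg atrophy from girth change common to both thighs. This follows from the text without any numerical assumption.

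The size of any precision loss is not established. Under an assumed same-visit correlation of 0.95, the variance ratio runs from 1.0 to 2.0 as the correlation with the preoperative healthy thigh falls from 0.95 to 0.90. It applies only if the outcome is a raw difference from the preoperative healthy value. The possibility that common change differs by arm rests on the protocol's own expectation about activity, and is a matter of interpretation, not a demonstrated bias. The outcome is not primary and nothing in the sample size depends on it, so this is a minor, inexpensive improvement.

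**What to change.** In item 4 and in the thigh row of Table 1, add the healthy thigh at the same two levels at every postoperative visit where the operated thigh is measured. Keep the preoperative pair as baseline. Report two results side by side: the same-visit operated-minus-healthy difference, and the change from the operated leg's own preoperative value. State that the first does not replace the second.

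The cost is about a minute with a tape at visits that already take place, and two more form fields per visit. Every analysis possible under the present schedule stays possible. The downside is interpretive: the healthy thigh may change after surgery, so the two results can disagree. Showing both makes that visible.

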We hypothesize that subjects randomized to receive the KRONOS postoperative unloader knee brace will reach full extension sooner and have reduce extension deficits compared to subjects randomized to receive the standard Breg T-scope hinged brace. In addition, it is hypothesized that the KRONOS subjects will require fewer additional treatments for extensions deficits including, but not limited to, additional therapy, intra-articular injections, oral corticosteroids, manipulation under anesthesia, or arthroscopic revision surgery.

Selection of Subjects –

Patients scheduled to undergo primary ACL reconstruction as indicated via CPT 29888 from the Athena electronic medical record (EMR) will be identified and eligible for enrollment in this study. Following the informed consent process outlined below, we will prospectively enroll and randomize 20 participants to one of the two study arms (KRONOS versus Breg T-scope post-operative knee brace), totaling 40 participants in each group.

Inclusion Criteria:

- Subjects > 18 years of age
- English-speaking
- Scheduled to undergo primary anterior cruciate ligament reconstruction surgery
- No history of prior knee surgery on the operative knee
- No concomitant ligamentous repair or reconstruction procedures (i.e. ligamentous pathology aside from anterior cruciate ligament).
- Subjects undergoing concurrent partial meniscectomy or meniscus repair that would not alter postoperative weight-bearing status or rehabilitation protocol would be eligible for inclusion.

Version 2.0: 4/25/2025 Page 3 of 11

• Clinical and radiographic examination (MRI) consistent with an acute full thickness ACL tear

Exclusion Criteria:

- Age < 18 years of age
- Non-English speaking
- Revision ACL reconstruction
- Multi-ligamentous injury, including concomitant posterior cruciate ligament, medial collateral ligament and fibular collateral ligament injuries
- Concomitant meniscal or cartilage injury that would alter postoperative weight bearing status or rehabilitation protocol
- Inability to comply with the proposed follow-up clinic visits
- Subjects lacking decisional capacity
- Worker's compensation subjects
- Requiring a custom-sized brace

Consent process -

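### The protocol says the trial will help show whether KRONOS is safe, but no brace-related harm is a named variable, none of the listed harm outcomes covers KRONOS-only preoperative wear, and 20 patients cannot support an unqualified claim of safety

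*Protocol*

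**What the plan says.** **Safety statement.** The Protocol, Risk/benefit assessment, says: "This study will help determine if the KRONOS postoperative knee brace is an efficacious and safe methodology".

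**Exposure.** Under Bracing Protocol, KRONOS Bracing Group, the brace is fitted at the first clinic visit after enrolment, and "The patient will be instructed to use the brace preoperatively and bring it to their surgery". The Table 1 footnote attached to preoperative brace placement reads: "Only for patients randomized to the KRONOS brace treatment group". The control brace is applied in the operating room. Timeline of Events, item 8, however, puts fitting for both braces on the day of surgery.

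**Harm outcomes.** Under Retrospective Data Collection, the list begins "The following outcome variables will be taken from Athena and Patient IQ". Its harm-type entries are complications after surgery (not defined), failure of the primary reconstruction, and revision or a subsequent procedure.

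**Other data that bear on harm.** Range of motion is examined at the initial visit, on the day of surgery and under anesthesia (Timeline, item 3). VAS pain is collected before surgery and at 12 weeks, 6 months and 12 months (items 5 and 10). A knee examination of unspecified content is made at every follow-up visit (item 9). A survey asks about compliance with bracing instructions (item 6). On laxity, item 2 says: "Pre-operative physical exam findings including Pivot-shift, Lachman, and range of motion data will be recorded".

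**Monitoring.** Data & Safety monitoring says: "There is minimal risk to the subjects except the potential for loss of privacy and confidentiality".

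**Size.** Study Design & Procedures says: "We estimate 40 participants (20 Kronos: 20 T-Scope) will be enrolled in the study". Selection of Subjects instead ends with "totaling 40 participants in each group".

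**The concern.** A reader is told that the trial will inform safety, but the protocol names no variable that records a problem caused by the brace in either arm. The harm outcomes it does name start at surgery and depend on what clinicians happened to write down. If the Bracing Protocol section is followed, one arm wears its device during a period that none of those outcomes covers.

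At stake is the interpretation of an empty harm table. A chart review with no brace-related entries could mean that there were no problems, or that nobody asked. With about 20 exposed patients, even complete recording would leave fairly common harms compatible with the data. The primary endpoint and its test are not affected.

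**Working it through.** **1. What the sample size was built for.** The only stated calculation concerns extension loss (Data Analysis and Statistical Considerations): p1 = 0.545, p2 = 0.091, alpha 0.05, power 0.80, 32 in total, raised to 40. The total can be reproduced with the pooled two-proportion formula, two-sided, without continuity correction:

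- n per arm = [1.96·√(2·p̄·(1−p̄)) + 0.842·√(p1(1−p1) + p2(1−p2))]² / (p1−p2)²
- p̄ = (0.545 + 0.091)/2 = 0.318
- First term: 1.96 × √0.4338 = 1.291. Second term: 0.842 × √0.3307 = 0.484.
- n = (1.291 + 0.484)² / 0.454² = 3.150/0.2061 = 15.3, rounded up to 16 per arm, so 32 in total
- 32/(1 − 0.20) = 40, so the increase corresponds to 20% loss

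The protocol names Fisher's exact test, so this reproduces the total rather than the named method. Either way, no harm rate enters the calculation.

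**2. Which listed outcome covers which period.**

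| Period | KRONOS | T-Scope | Listed harm outcome | Incidental sources |
|---|---|---|---|---|
| First fitting to surgery | worn (Bracing Protocol) | not worn | none | day-of-surgery exam, preoperative VAS pain, chart |
| Surgery to 12 months | worn | worn | complications, reconstruction failure, revision or further procedure, all from records | follow-up knee exam, VAS pain, survey |

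The brace survey row of Table 1 also appears to carry a KRONOS-only mark around surgery. The table is broken in the text at hand, so this is uncertain, and the stated content of the survey is compliance. No row contains a named brace-problem variable.

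**3. What zero events would exclude.** If 0 of n patients have an event, the exact upper limit is 1 − 0.05^(1/n) (one-sided 95%) or 1 − 0.025^(1/n) (two-sided 95%).

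| n on KRONOS | One-sided | Two-sided |
|---|---|---|
| 20 (as enrolled) | 13.9% | 16.8% |
| 16 (completers, per the plan's own allowance) | 17.1% | 20.6% |
| 40 (if the Selection of Subjects wording were meant) | 7.2% | 8.8% |

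These limits assume that every event is recorded. If some events never reach the record, the limit applies only to the recorded rate, and the limit on the true rate is higher.

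**4. Chance that a real harm is not seen at all in 20 patients**, (1 − rate)^20:

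- 1%: 0.99^20 = 0.82
- 2%: 0.98^20 = 0.67
- 5%: 0.95^20 = 0.36
- 10%: 0.90^20 = 0.12
- 15%: 0.85^20 = 0.04

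**5. Comparison between arms.** The protocol gives no harm rates, so these are assumptions. With 20 per arm and a two-sided Fisher test at 0.05, power is 1.7% for 5% against 10%, and 17% for 5% against 20%. Reaching 80% power against a 5% control rate needs about 44.5% in the other arm.

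**The case against.** The strongest reply is that safety is not an objective here. The stated purpose is clinical efficacy, the hypotheses, primary outcome and power analysis contain no safety question, and the word *safe* appears once, softened by the verb *help*. No analysis or rule would declare the brace safe. A trial of 40 need not be powered for harms, and the zero-event limits apply to any arm of 20. All of that stands, and it makes this a point about one sentence and one missing data item, not a fault in the main comparison.

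Four stronger readings are tempting, and the document does not support them.

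- *Complications are the only harm outcome.* Reconstruction failure and revision or further procedures are also listed.
- *Preoperative harms would be missed altogether.* The day-of-surgery examination, preoperative VAS pain and chart abstraction could record them. They are simply not collected as an outcome.
- *Graft laxity goes unexamined after surgery.* Lachman and pivot-shift are named only before surgery, but a knee examination is required at every follow-up visit and nothing excludes those tests. Naming them would be an optional clarification.
- *The protocol says privacy is the sole risk.* It describes risk as minimal apart from privacy, and consent pages, where device risks would normally appear, are not in the text at hand.

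The items of the brace survey are also not shown, so it cannot be proved that no question touches on brace problems. What can be said is that the protocol describes it as a compliance survey.

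That the statistical analysis plan is not at hand is no answer. Which data are collected, and from when, is fixed by the protocol, and an analysis plan cannot recover an item that was never asked.

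**Conclusion.** The point holds in a limited form. The protocol offers to inform safety, yet it names no brace-related harm variable, its harm outcomes are all postoperative and record-based, and the wear that only KRONOS patients have before surgery lies outside them. As written, the trial could not compare brace problems between arms on data collected for that purpose.

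With 20 KRONOS patients, zero events would exclude only rates above about 14% (one-sided) to 17% (two-sided). A 5% harm would be absent 36% of the time and a 10% harm 12% of the time. Very common harms would probably be seen. Anything rarer could not be ruled out, so an unqualified statement of safety would not be justified. Even on the conflicting reading of 40 per arm, the limits are 7.2% and 8.8%.

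These figures assume independent patients, complete recording, and 20 patients who actually wear the brace. The preoperative part also assumes that the Bracing Protocol section is the intended one. If the Timeline's day-of-surgery fitting were intended, the preoperative gap would shrink or disappear, while the missing variable and the limited precision would remain.

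**What to change.** 1. Add one brace-problem item to the existing brace survey and to the visit form, in both arms, from first fitting through 12 months and including the day-of-surgery visit. Where the survey is not scheduled, the visit form carries it.
2. Report the number of patients with a brace problem per arm, with exact 95% limits and the number who wore the brace as denominator. Show the preoperative period separately, because only one arm may be exposed then.
3. Reword the sentence in Risk/benefit assessment so that safety is described rather than determined. Wording to this effect would do: brace-related problems will be summarized by arm with exact 95% confidence limits, and the trial is not designed to establish safety.
4. Reconcile the KRONOS Bracing Group text and Table 1 footnote with Timeline of Events, item 8, so that the start of exposure is unambiguous. Which of them is intended is for the investigators to say.

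The cost is one extra item per visit and a weaker safety statement. Sample size, primary endpoint and visit schedule stay as they are.
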